Aim 2. Quantify the relationship between function, pain symptomology, and disease severity. Hand function, clinical and experimental pain, and disease severity will be measured in adults with end-stage CMC OA, age-matched controls, and young-healthy individuals. We *hypothesize* individuals with CMC OA will demonstrate greater functional deficits and higher experimental pain sensitivity than age-matched controls and young-healthy individuals. Additionally, in individuals with CMC OA, we hypothesize that functional loss will be associated with higher clinical pain, but not necessarily higher disease severity. Completion of this aim will comprehensively and quantitatively characterize the multi-faceted symptomology of CMC OA and provide insights into the somatosensory mechanisms affecting this disease.

6. RESEARCH PLAN:

Sample Size & Justification: A total of 60 subjects will complete the proposed research study: 20 individuals with end-stage CMC OA, 20 age-matched controls, and 20 young-healthy individuals. These subjects will represent the racial and ethnic diversity of the state of Florida. Vulnerable populations including pregnant women and prisoners will be excluded. All subjects will be between the ages of 18 to 90. Specifically, the end-stage CMC OA cohort and age-matched controls will be between the ages of 40 to 90 as CMC OA is most prevalent in older adults. While the young-healthy cohort will be between the ages of 18-39. A power analysis ($\alpha = 0.05$, $1-\beta = 0.80$) to detect 20% differences in pinch strength between groups required 15 individuals per cohort. Due to including a young-healthy cohort and to prevent erroneous inferences to occurs after multiple comparisons, 20 individuals per cohort will be recruited. Note, pinch strength was the only relevant variable for which standard deviations could be consistently estimated from the literature.^{23, 36} Thus, an important outcome of this pilot project will be the data necessary to robustly estimate sample sizes for future studies. For reference, prior studies indicate that individuals with early-stage CMC OA have 20-30% less pinch strength than controls.^{23, 36}

A summary of inclusion and exclusion criteria are provided below:

Inclusion Criteria:

CMC OA Subjects:

- female between the age of 40 to 90 years
- end-stage CMC OA diagnosed by a board-certified clinician

Age-Matched Control:

- female between the age of 40 to 90 years
- no joint or muscle pain in the hand or wrist

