locations. The flyer will provide potential participants with the information necessary to contact the Study Team by phone and/or e-mail.

- 2) Website Advertisement – An IRB-approved recruitment message will be posted on the Principal Investigator's Lab Website (<https://www.bme.ufl.edu/labs/[name]/get-involved/>) The recruitment message will provide potential participants with the information necessary to contact the Study Team by phone and/or e-mail.
- 3) Word of Mouth – The Principal Investigator and Study Team frequently share results from completed studies through invited talks, guest lectures in undergraduate and graduate courses, and community events. When discussing our human subjects research, one of the most commonly asked questions is whether there are opportunities to become involved as a study participant. Thus, we will share information about the study verbally with interested members of the community. When such verbal conversations take place, we will provide the potential participants with the information necessary to contact the Study Team by phone and/or e-mail. Scheduling and enrollment will occur at least 48 hours after the initial conversation and only after the potential participant has proactively contacted the Study Team.

Initial Contact with Study Team:

When a potential participant contacts the Study Team, we will follow-up with the potential participant by phone or e-mail. During that discussion, we will ask the following questions:

- a) Are you a female between 18 and 90 years old?
- b) Have you been diagnosed with arthritis in your hand or wrist?
- c) Do you currently have muscle or joint pain in the hand or wrist?
- d) Have you had any muscle or joint pain in your hand or wrist requiring medical attention or physical therapy in the last 6 months?
- e) Are you currently pregnant, mentally disabled, incarcerated, on parole, on probation, or awaiting trial?
- f) Do you have any systemic musculoskeletal, neurological, or autoimmune diseases, such as diabetes, rheumatoid arthritis, or stroke?

If a potential participant answers "yes" to question (a) and "no" to questions (b) – (f), then we will proceed with scheduling a study visit as an age-matched control subject.

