If a potential participant answers "yes" to question (a) – (b) and "no" to questions (c) – (f), then we will ask the following follow-up question: "What kind of arthritis have you been diagnosed with in your hand or wrist?" If the answer is thumb OA, we will proceed with scheduling a study visit as an CMC OA subject.

Otherwise, the potential participant will be informed that he or she is ineligible to participate.

To facilitate continued communication and follow-up, we will ask the potential participant what his or her preferred method of contact is and will record his or her name, phone number, and e-mail address during these initial conversations. We will use the e-mail address to provide the potential participant with an electronic copy of the informed consent form to review prior to his or her first visit. This copy of the informed consent form will be provided to the subject at least 24 hours prior to their scheduled participation. All research subjects will be consented in-person at the time of their first study session.

Enrollment & Informed Consent:

Prior to experimental data collection, each participant will be given the opportunity to review the informed consent form and study procedures in-person with a member of the study team. This discussion will include information on study purpose and procedures, benefits and risks, who to contact (study team, IRB, etc.), that participation is voluntary and participants can withdraw at any time, HIPAA and confidentiality, as well as cost and compensation. The participant will be given the opportunity to ask questions. After all questions have been answered, the participant will sign the informed consent form, documenting that they provide consent to participate as well as authorization to access their private health information as outlined on the informed consent form.

Research Approach:

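### The screening rule for self-referred women books a woman with thumb OA as a CMC OA subject only if she reports no hand or wrist pain, which contradicts the written CMC OA criteria

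*Protocol*

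**What the plan says.** Protocol section 6 describes two ways into the CMC OA cohort. The main one is the hand clinic, where a clinical member of the team identifies women who meet the inclusion criteria and approaches them at the end of their visit. The other is self-referral by flyer, website or word of mouth. The Recruitment text expects self-referral to yield mainly age-matched controls, but it says that people with CMC OA may also come this way.

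Self-referred women are asked questions (a) to (f) under Initial Contact with Study Team. Question (c) is "Do you currently have muscle or joint pain in the hand or wrist". Question (d) asks about hand or wrist pain "requiring medical attention or physical therapy in the last 6 months". A caller with an arthritis diagnosis goes forward only if she answers yes to (a) and (b) and no to all of (c) to (f). She is then asked what kind of arthritis she has: "If the answer is thumb OA, we will proceed with scheduling a study visit as an CMC OA subject". For all remaining answer patterns the rule is "Otherwise, the potential participant will be informed that he or she is ineligible to participate".

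The Inclusion Criteria list two conditions for CMC OA subjects: "female between the age of 40 to 90 years" and "end-stage CMC OA diagnosed by a board-certified clinician". Neither mentions pain. Freedom from hand and wrist pain is listed for the age-matched controls and for the young-healthy group. The exclusions for all groups do not mention pain, and they exempt osteoarthritis from the excluded hand and wrist pathologies.

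**The concern.** The screening rule adds a condition, no reported hand or wrist pain, that the written CMC OA criteria do not contain. Nothing in the protocol describes a pain-free CMC OA cohort. Section 5 opens with symptomatic CMC OA, and Aim 1 relates the level of pain during tasks to muscle activity, joint angles and joint stability. The Plain Film Radiographs text ties recruitment on lack of pain to the control subjects.

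Two things are at stake. First, women who meet the written criteria and volunteer are told they are ineligible, and no later analysis can recover them. Second, the two routes would select differently on pain. Section 4 states that pain is the main complaint of people seeking treatment for CMC OA, so a woman who attended a hand clinic for thumb pain in the last 6 months would be expected to answer yes to (d). The screen thus refuses the kind of woman the clinic route enrols. Pain within the CMC OA cohort would then depend in part on how a subject was recruited, while the Clinical Pain & Psychological Measure text makes clinical pain metrics primary outcome variables. Self-referred subjects would tend to pull the cohort toward the control level.

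**Working it through.** The check is one of logic. The plan gives no figure here to reproduce.

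**Inputs, all from Protocol section 6.** The answer rules come from Initial Contact with Study Team, the eligibility conditions from Inclusion Criteria and Exclusion Criteria, and the cohort size of 20 from Sample Size & Justification.

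**Step 1: trace one woman through both rules.** Take a woman aged 40 to 90 with clinician-diagnosed end-stage CMC OA and none of the listed exclusions. She answers yes to (a), yes to (b) with thumb OA as the type, and no to (e) and (f). Only her answers on pain vary.

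| Case | (c) current pain | (d) pain needing care, last 6 months | Written criteria | Screening rule |
|---|---|---|---|---|
| 1 | no | no | met | booked as CMC OA |
| 2 | yes | no | met | ineligible |
| 3 | no | yes | met | ineligible |
| 4 | yes | yes | met | ineligible |

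The two rules agree in case 1 only. A yes to either pain question is enough for refusal.

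**Step 2: count the pain conditions.**
- Screening rule, CMC OA branch: 2 of 2 pain questions must be answered no.
- Written CMC OA inclusion criteria: 0 of 2 concern pain.
- Written criteria for each control group: 1 of 2 concerns pain.

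The CMC OA branch requires the same answers to (c) to (f) as the control branch does. Only the answer to (b) and the follow-up question differ.

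**Step 3: compare the other two conditions.** Question (a) is "Are you a female between 18 and 90 years old", while the CMC OA cohort is restricted to 40 to 90. The follow-up asks only for the type of arthritis, not whether a clinician has diagnosed end-stage disease. These are gaps in the screen rather than in eligibility, because the inclusion criteria still apply to everyone counted in the cohort.

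**Step 4: possible weight in the cohort.** If k of the 20 CMC OA subjects are self-referred, their weight in a cohort mean is k/20. The protocol does not state k, so the values below are assumptions.

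| k | weight |
|---|---|
| 0 | 0/20 = 0% |
| 1 | 1/20 = 5% |
| 2 | 2/20 = 10% |
| 4 | 4/20 = 20% |

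The arithmetic limit is k = 20 (100%), but the Recruitment text points to a small k. These are weights, not sizes of bias. A bias would also need the difference in pain between the two routes, which the protocol does not give.

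**The case against.** The strongest reply is that very little passes through this screen. The protocol recruits CMC OA subjects directly from the hand clinics, and those women never meet these questions. Self-referral is listed as a way to find controls, and the cohort of 20 could be filled with none entering by it. The effect on results is then conditional and unsized, and k/20 holds for any subset of 20. This stands. It limits the reach of the point but does not remove the contradiction: the protocol writes a separate branch for these callers, and even at k = 0 the branch refuses women it should admit.

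A second reply is that a pain-free woman with end-stage CMC OA is not wrongly admitted, since the written criteria do not require pain. Alongside clinic subjects, a few women with little pain might even widen the range of pain available for the association analyses in Aims 1 and 2. This also stands, and no narrowing of the pain range in the whole cohort is claimed. Nor does a no at the call rule out movement-evoked pain or non-zero questionnaire scores. The defect is that painful cases are refused, not that painless ones are accepted.

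Third, the contrast with the clinic route rests partly on inference. Section 4 makes a general statement about people seeking treatment, and the clinic route does not require pain. That is fair, but the conflict between the screen and the inclusion criteria does not depend on it.

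Finally, question (f) gives diabetes without qualification as an example of a disqualifying disease, whereas the exclusion is for uncontrolled diabetes. This is a separate mismatch in the same questions. It would remain after (c) and (d) are corrected, but it does not make that correction unsound.

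**Conclusion.** The contradiction is plain on the text, and no other part of the protocol resolves it. Followed as written, the screen refuses self-referred women who meet the CMC OA criteria whenever they report current hand or wrist pain, or such pain needing care in the last 6 months. Any CMC OA subjects it does admit are selected for reporting neither.

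The size is bounded but not known. Only the self-referral route is affected. The number of women refused cannot be stated. The possible effect on cohort means depends on k, which the protocol does not give, and on a difference in pain between routes, for which it gives no figure. The expectation that self-referred subjects would report less pain assumes that clinic patients largely come because of pain, as section 4 suggests.

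This should be fixed: the inconsistency is certain and bears on eligibility in a study with pain among its primary outcomes, though its likely reach is small.

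**What to change.** Reconcile the CMC OA branch under Initial Contact with Study Team with the Inclusion Criteria and Exclusion Criteria:

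- For women who report thumb OA, remove no to (c) and (d) as a condition. Keep it for the control groups. Add no requirement that pain be present.
- In that branch, ask instead about the hand and wrist pathologies other than osteoarthritis that are already excluded, such as distal radius fracture, contracture, trigger finger and carpal tunnel.
- Apply the existing 40 to 90 age range in that branch.
- Confirm the existing criterion of clinician-diagnosed end-stage CMC OA before a self-referred woman is counted in the CMC OA cohort.

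The wording on diabetes in question (f) can be aligned with the written exclusion in the same amendment.

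The cost is an IRB amendment to the wording of the screening questions and one confirmation step for self-referred women. No extra subjects are needed, and every criterion used is already in the protocol.

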Young-Healthy Subjects:

- female between the age of 18 to 39 years
- no joint or muscle pain in the hand or wrist

Exclusion Criteria:

All Groups:

- Pregnant women; minors (under age 18); mentally disabled; any persons incarcerated, on parole, on probation, or awaiting trial
- Individuals with concomitant musculoskeletal pathologies (other than osteoarthritis) in the hand or wrist, including distal radius fracture, contracture, trigger finger, and carpal tunnel
- Individuals with history of uncontrolled diabetes, rheumatoid arthritis, muscular dysfunction, or neurological disease

Recruitment:

The CMC OA subjects, age-matched control subjects, and young-healthy control subjects will be recruited, as described below:

CMC OA Subject Recruitment: Subjects with CMC OA will be recruited directly from the hand clinics at the UF Orthopaedics Sports Medicine Institute (OSMI). Specifically, a clinical member of the study team affiliated with the Department of Orthopaedics (e.g., [name]) will identify individuals who meet the inclusion criteria. These individuals will be asked at the end of their clinic visit if they are interested in learning more about the research study and potentially participating. At this time, the potential participant's contact information (name, e-mail, phone number) and preferred contact method (phone or e-mail) will be recorded. A member of the IRB-approved study team will then reach out to the potential participant by phone or e-mail to discuss the study and answer any questions. If the potential participant expresses interest, he or she will be e-mailed a copy of the informed consent document to review and discuss with their friends and/or family. The study sessions will also be scheduled at this time. Subjects will be consented in-person at the time of their first study session.

Age-Matched Control Subjects and Young-Healthy Subjects: Age-matched control subjects and young-healthy subjects will be recruited using the mechanisms listed below. It should be noted that individuals with CMC OA may also contact the study team via these mechanisms. However, the study team anticipates that these mechanisms will more readily identify age-matched control subjects:

- 1) Recruitment Flyer – An IRB-approved recruitment flyer will be posted around the University of Florida's campus and the Gainesville community in approved advertising

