Participants will perform range of motion (thumb only) and strength (pinch and grip) tests as well as the Jebsen Hand Function test, which includes seven timed activities to evaluate fine and gross motor function. Participants will also complete the Disability of arm, shoulder, hand (DASH) score, a widely used functional outcome measure for the upper limb. Together, these measures were chosen to provide insights into strength, range of motion, as well as fine and gross motor function.

Session III – Medical Imaging Session (Collection of Data for Aim 2)

Location: Plain film radiographs will be collected at the Orthopaedic Sports Medicine Institute (OSMI) located at [name].

Testing Procedure: Plain film radiographs will be acquired to assess disease severity. Acquisition methods will be similar to those used for clinic patients:

Plain Film Radiographs.

For each subject, radiographs will be acquired from two views: anteriorposterior (Robert view) and lateral view. For the CMC OA subjects, if the x-ray views required for this study have been acquired as part of a standard clinical visit in the last 1 month, new x-rays will not be acquired as part of the study. Instead, x-rays will be obtained from the subject's medical record, following informed consent and approval. A certified UF Health technician will acquire the films. According to RadiologyInfo.org, an information service sponsored by the Radiological Society of North America (RSNA) and the American College of Radiology (ACR), an x-ray of an extremity (such as the hand or foot) has an approximate radiation dose of 0.001 mSv, which is equivalent to approximately 3 hours of natural background radiation (<https://www.radiologyinfo.org/en/info.cfm?pg=safety-xray>). Given that this study will require two x-rays, we estimate the approximate radiation dose as 0.002 mSv, or the equivalent of 6 hours of natural background radiation. The radiographs will be used to classify the presence of CMC OA using the Eaton classification method and the Hand OA Index. The control subjects will be recruited based on lack of pain and disability. These asymptomatic subjects may have evidence of CMC joint degeneration, which will be an important covariate in the analyses. The severity of CMC OA within the CMC OA participants will also be important for analyzing the experimental and clinical pain as well as functional measures in the context of disease severity.

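### The self-referral phone script schedules callers as CMC OA subjects without checking joint, stage or clinician diagnosis, and no later step is stated to apply the end-stage criterion

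*Protocol*

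**What the plan says.** All references are to the protocol.

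- **Cohort definition** (section 6, Inclusion Criteria, CMC OA Subjects): women aged 40 to 90 with "end-stage CMC OA diagnosed by a board-certified clinician". The sample-size paragraph repeats the age range: "the end-stage CMC OA cohort and age-matched controls will be between the ages of 40 to 90". Both aims in section 5 are stated for adults with end-stage disease.
- **Clinic route** (Recruitment): subjects come from the hand clinics, where a clinical member of the team "will identify individuals who meet the inclusion criteria".
- **Self-referral route** (Recruitment): flyer, website and word of mouth are described for the two control groups, but "It should be noted that individuals with CMC OA may also contact the study team via these mechanisms". The protocol adds that "the study team anticipates that these mechanisms will more readily identify age-matched control subjects".
- **Phone script** (Initial Contact with Study Team): the disease question is (b), "Have you been diagnosed with arthritis in your hand or wrist". A caller who answers yes to (a) and (b) and no to (c) to (f) is then asked what kind of arthritis it is. The rule that follows is: "If the answer is thumb OA, we will proceed with scheduling a study visit as an CMC OA subject". Questions (c) and (d) concern current hand or wrist pain, and such pain needing care in the last 6 months. Question (a) accepts women aged 18 to 90.
- **Imaging** (Plain Film Radiographs): "The radiographs will be used to classify the presence of CMC OA using the Eaton classification method and the Hand OA Index".

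**The concern.** The inclusion criterion has three parts: end-stage, at the CMC joint, and diagnosed by a qualified clinician. On the clinic route, someone competent to judge them does so. On the self-referral route, the only disease information described is the caller's own report. Thumb OA carries no stage and does not name the joint, and the thumb has joints other than the CMC. She must say she has been diagnosed, but she is not asked by whom, and nothing is said about confirming it.

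If no step applies the criterion, the two routes can bring different disease into one cohort of 20, and results reported for end-stage CMC OA may describe a mixed group. Aim 2 relates function and pain to disease severity within the CMC OA subjects, so an uncontrolled stage mix goes to the centre of that aim. If the gap is noticed only when the films are graded, any decision to keep or drop a subject would be unplanned and made with her data in hand.

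**Working it through.** **1. The two routes against the criterion.**

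| Part of criterion | Clinic route | Self-referral route |
|---|---|---|
| CMC joint | judged by a clinical team member | not asked; 'thumb OA' is enough |
| End-stage | judged by a clinical team member | not asked |
| Clinician diagnosis | judged by a clinical team member | self-reported diagnosis; clinician not asked, no confirmation stated |
| Age 40 to 90 | judged by a clinical team member | question (a) accepts 18 to 90 |

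**2. Search for a later check.**

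- Enrollment & Informed Consent covers consent and authorization to access health information. It describes no eligibility check.
- Research Approach lets the sessions run in any order, so the films may follow all other testing.
- Plain Film Radiographs uses the films to classify disease and to analyse severity. It gives no rule for a CMC OA subject whose disease is not end-stage. Films from the medical record serve only to avoid repeat imaging.
- Section 7 lets the study physician exclude people at excessive risk. That is not a check of diagnosis or stage.

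None of these applies the inclusion criterion to a self-referred caller.

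**3. Scale if some subjects do not have CMC disease.** The protocol gives no number of self-referred CMC OA subjects, so 2, 4 and 6 of 20 are assumed. Each such subject is also assumed to have no pinch deficit. This is a worst case, since thumb OA at another joint may itself weaken pinch.

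Apparent deficit = (20 − k)/20 × 20%:

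- k = 2: 18/20 × 20% = 18%
- k = 4: 16/20 × 20% = 16%
- k = 6: 14/20 × 20% = 14%

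The protocol's 15 per cohort (20% difference, alpha 0.05, power 0.80) cannot be reproduced, because no SD is given. Solving backwards from n = 2 × (1.960 + 0.842)² × CV² / 20², two-sided, n rounds up to 15 for a CV of about 18.9% to 19.6% of the control mean. The power for 20 per cohort is then Φ(d / (CV × √(2/20)) − 1.960), for CVs of 18.9% and 19.5%:

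| Subjects without CMC disease (assumed) | d | Power |
|---|---|---|
| 0 of 20 | 20% | 0.90–0.92 |
| 2 of 20 | 18% | 0.83–0.85 |
| 4 of 20 | 16% | 0.74–0.76 |
| 6 of 20 | 14% | 0.62–0.65 |

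These figures use an unadjusted alpha of 0.05 and hold the CV fixed.

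**4. Scale if some subjects have early-stage CMC disease.** The protocol's cited deficit of 20% to 30% is itself from early-stage disease. With k early-stage subjects at deficit e and the rest at E, the cohort mean is [(20 − k)E + k·e]/20. If e is at least 20% and E is at least 20% (an assumption, as no end-stage figure is given), the mean is at least 20% for every k. Early-stage entrants therefore need not pull the pinch contrast below the difference the study was sized for. What they change is whom the cohort represents.

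**The case against.** The strongest reply is that this is a phone pre-screen. Its outcome is a scheduled visit, it does not waive the inclusion criterion, and it is evidently not the full eligibility check: it also omits the age floor of 40 and exclusions such as fracture and trigger finger. The films are graded for every subject, so a misplaced subject would be visible. Clinic recruitment is the main source of CMC OA subjects, and the other route is expected to find mostly controls.

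Much of this stands. A reader might infer that any caller who mentions thumb OA is enrolled in the end-stage cohort. The documents do not support that: she must also pass (c) to (f), she is scheduled rather than enrolled, and the criterion formally remains in force. A reader might also infer that early-stage entrants weaken the powered comparison. The protocol's own figures do not support that either.

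The reply does not supply the missing step. The script assigns the cohort when it schedules the visit, the clinic route states who applies the criterion, and this route states no one. Grading films makes a misplaced subject visible, but no rule says what follows. An analysis plan could handle severity in the models; eligibility and cohort assignment belong in the protocol.

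**Conclusion.** The point holds in limited form. For self-referred callers, the protocol's scheduling rule does not match its cohort definition, and no stated step closes the gap. Women with early-stage or non-CMC thumb OA could be counted among the 20 end-stage subjects.

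The number is unknown and probably small. The firm harm is to the end-stage definition of the cohort and to the Aim 2 severity analyses. Dilution of the case-control contrasts follows only where the disease is not at the CMC joint. Under the worst-case assumptions above, two such subjects leave power above 0.80 and four take it below; those counts and the CV are assumptions, not protocol figures.

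Two further mismatches sit in the same script. Questions (c) and (d) let through only callers without current hand or wrist pain and without such pain needing care in the last 6 months, although the aims concern the symptoms of the disease. Question (a) accepts ages 18 to 90 for a cohort limited to 40 to 90.

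**What to change.** Amend Initial Contact with Study Team as follows.

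1. A self-referred caller is counted in the CMC OA cohort only after a clinical co-investigator confirms the existing inclusion criterion. Confirmation comes from her medical record, with authorization, or from the study films taken first after consent.
2. A self-referred subject who does not meet the criterion is not counted in that cohort and is replaced.
3. Reconcile questions (a), (c) and (d) with the cohort's age range and with the symptomatic disease that the aims address.

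The rule should be limited to self-referred subjects and rest on the clinician's diagnosis. The protocol sets no radiographic threshold for end-stage, so a rule based on film grade alone could override the diagnosis of women recruited in clinic.

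The cost is a short change to protocol and script. Record access, films and a clinical co-investigator are already in the study. Self-referred subjects may lose free choice of session order, and a few may be screened out after consent.
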